3.5.1.2 Handling of Dropouts and Missing Data

It is anticipated that the main cause of missing data for the primary analysis will be subjects who discontinue early as a result of death due to their underlying disease in the ICU. If no *P aeruginosa* pneumonia occurs prior to discontinuation, the subject will be considered having no *P aeruginosa* pneumonia infection in the primary efficacy analysis. No other imputation will be applied to the primary efficacy analysis.

Redacted
ed

Redacted

Redacted

Redacted

Redacted

Redacted
ed

- Redacted
- Redacted
- Redacted

Redacted

- Redacted
- Redacted

Redacted

Redacted

Redacted

Redacted

[figure not shown]
Redacted

[figure not shown]
Redacted

Redacted

Redacted

Redacted

Redacted
[Redacted text block]

[Redacted text block]

Redacted
[Redacted text block]

[Redacted text block]

Redacted
[Redacted text block]

Redacted
[Redacted text block]

[Redacted text block]

Redacted
[Redacted text block]

Redacted
[Redacted text block]

[Redacted text block]

[Redacted text block]

[Redacted] Redacted
[Redacted text block]

Redacted
[Redacted text block]

- [Redacted]
- [Redacted]
- [Redacted]
- [Redacted]

[Redacted text block]

Redacted
[Redacted text block]

Redacted
[Redacted text block]

[Redacted text block]

Redacted
[Redacted text block]

[Redacted text block]

[Redacted text block]

Redacted
[Redacted text block]

[Redacted text block]

[Redacted text block]

Redacted [redacted]
[redacted]
[redacted]
[redacted]
[redacted]
[redacted]

[redacted]
[redacted]
[redacted]
[redacted]
[redacted]
[redacted]
[redacted]
[redacted]
[redacted]
[redacted]
[redacted]

[redacted]
[redacted]
[redacted]
[redacted]
[redacted]
[redacted]
[redacted]
[redacted]
[redacted]
[redacted]

[redacted]
[redacted]
[redacted]
[redacted]

[redacted]
[redacted]

[redacted]
[redacted]

[redacted]
[redacted]
[redacted]

Re [redacted]
dac [redacted]
ted [redacted]
[redacted]

[redacted]

[redacted]

[redacted]
[redacted]
[redacted]

[redacted]
[redacted]
[redacted]
[redacted]

[redacted] [redacted]
[redacted]
[redacted]
[redacted]
[redacted]
[redacted]
[redacted]
[redacted]
[redacted]
[redacted]
[redacted]
[redacted]
[redacted]
[redacted]
[redacted]
[redacted]
[redacted]
[redacted]
[redacted]
[redacted]

Redacted [redacted]
[redacted]

[redacted] [redacted]
[redacted]
[redacted]

[redacted] [redacted]
[redacted]
[redacted]

Redacted
[Redacted text block]

[Redacted text block]

[Redacted text block]

[Redacted text block]

[Redacted text block]

[Redacted text block]

[Redacted text block]

[Redacted text block] Redacted

[Redacted text block]

Redacted
[Redacted]
[Redacted]
[Redacted]

[Redacted]
[Redacted]

[Redacted]

[Redacted]

cted
[Redacted]

[Redacted]

[Redacted]

[Redacted]

[Redacted]

[Redacted]

[Redacted]

[Redacted]

[Redacted]

[Redacted]

[Redacted]

[Redacted]

[Redacted]

[Redacted]

[Redacted]

[Redacted]

[Redacted]

[Redacted]

[Redacted]

[Redacted]

[Redacted]

[Redacted]

[Redacted]

[Redacted]

[Redacted]

[Redacted]

Redacted

Redacted

[Redacted]

[Redacted]

[Redacted]

[Redacted]

Redacted

[Redacted]

[Redacted]

[Redacted]

[Redacted]

[Redacted]

[Redacted]

[Redacted]

[Redacted]

[Redacted]

[Redacted]

[Redacted]

[Redacted]

[Redacted]

[Redacted]

[Redacted]

[Redacted]

Redacted

[Redacted]

[Redacted]

[Redacted]

[Redacted]

[Redacted]

[Redacted]

[Redacted]

[Redacted]

[Redacted]

[Redacted]

Redac

Redacted

[Redacted]

[Redacted]

[Redacted]

[Redacted]

[Redacted]

[Redacted]

[Redacted]

[Redacted]

[Redacted]

[Redacted]

R
e
d
a
c
t
e
d

[Redacted text block]

3.8 Safety Analyses

3.8.1 Adverse Events and Serious Adverse Events

Adverse events (AEs) will be coded by MedDRA version 21.0 and the type incidence, severity and relationship to study investigational product will be summarized for subjects in the As-treated population by treatment group and for MEDI3902 total. Specific AEs will be counted once for each subject for calculating percentages. In addition, if the same adverse event occurs multiple times within a particular subject, the highest severity and level of relationship observed will be reported. All TEAEs will be summarized overall, as well as categorized by MedDRA System Organ Class and Preferred Term.

Serious Adverse Events (SAEs) will be summarized for each treatment group by MedDRA System Organ Class (SOC) and Preferred Term (PT).

The overall summary of AEs will summarise the number and percentage of subjects with at least one event, at least one investigational product related event, at least one event with at least Grade 3 severity, death due to AEs, at least one SAE, at least one serious and/or at least one Grade 3 severity event, at least one investigational product related serious event, at least one event leading to discontinuation of investigational product, at least one AESI, at least one investigational product related AESI, and at least one AESI \geq Grade 3 severity.

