Approximately 286 colonised subjects will be enrolled and randomised (1:1 ratio) to  $\frac{\text{Red}}{\text{r}}$  mg MEDI3902 (or in the case of dose adjustment,  $\frac{\text{Red}}{\text{r}}$  mg MEDI3902; n = 143) or placebo (n = 143).

Key assumptions used for sample size/power calculations: placebo group *P aeruginosa* pneumonia incidence 20%, relative reduction 50%, at least 80% power, 20% adjustment for attrition. Relative reduction of 50% was recommended to Sponsor as a clinically meaningful effect by experts in critical care, pulmonary medicine, and infectious diseases. In addition, 50% relative reduction was demonstrated in a study by Francois and colleagues (Francois et al, 2012) involving a monoclonal antibody to prevent *Pseudomonas* pneumonia in mechanically ventilated patients, supporting the biological feasibility of such an effect.

Power calculations are based on Poisson regression with robust variance comparing each MEDI3902 treatment group separately versus placebo, 2-sided, with  $\alpha = 0.2$ .

The sample size may be modified after approximately 50% of the subjects are enrolled and followed through 21 days postdose based on blinded assessment of the event rate and/or attrition rate in the overall population.

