# **1 INTRODUCTION**

# 1.1 Disease Background

*Pseudomonas aeruginosa (P aeruginosa)* is an important nosocomial pathogen, and pneumonia is one of its most important manifestations. Mechanical ventilation is the most important risk factor for nosocomial pneumonia caused by *P aeruginosa*, with cumulative risk increasing with the duration of ventilation (Zahar et al, 2009). In one study, *P aeruginosa* accounted for 13% of cases of microbiologically confirmed pneumonia acquired in the intensive care unit (ICU) by patients who were not mechanically ventilated, and 24% of cases in those who were (Esperatti et al, 2010). In a review of global epidemiology data, *P aeruginosa* caused approximately 27% of ventilator-associated pneumonia (VAP; Jones, 2010). Respiratory tract colonisation with *P aeruginosa* is another important risk factor (Rehm and Kollef, 2014). Despite the existence of antipseudomonal antibiotics, pneumonia, particularly VAP, due to *P aeruginosa* remains associated with significant mortality and morbidity, increased ICU and hospital length of stay, and substantial economic burden. Although general strategies exist to decrease the incidence of pneumonia in mechanically ventilated patients, there are no systemic agents approved for the prevention of pneumonia caused by *P aeruginosa*.

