# 2.2 Study Endpoints

#### 2.2.1 Primary Endpoint

Efficacy of MEDI3902:

1. Incidence of nosocomial pneumonia caused by P aeruginosa through 21 days postdose

Safety of MEDI3902:

1. Treatment-emergent AEs (TEAEs), treatment-emergent SAEs (TESAEs) and AESIs through 49 days postdose

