# 5 ASSESSMENT OF SAFETY

# 5.1 Definition of Adverse Events

The ICH Guideline for Good Clinical Practice E6(R1) defines an AE as:

Any untoward medical occurrence in a patient or clinical investigation subject administered a pharmaceutical product and which does not necessarily have a causal relationship with this treatment. An AE can therefore be any unfavorable and unintended sign (including an abnormal laboratory finding), symptom, or disease temporally associated with the use of a medicinal product, whether or not considered related to the medicinal product.

An AE includes but is not limited to any clinically significant worsening of a subject's preexisting condition. An abnormal laboratory finding (that requires medical intervention by the investigator, or a finding judged by the investigator as medically significant should be reported as an AE. If clinical sequelae are associated with a laboratory abnormality, the diagnosis or medical condition should be reported (eg, renal failure, hematuria) not the laboratory abnormality (eg, elevated creatinine, urine RBC increased). Abnormal laboratory values that are not, in the investigator's opinion, medically significant and do not require intervention should not be reported as AEs.

Adverse events may be treatment emergent (ie, occurring after initial receipt of investigational product) or nontreatment emergent. A nontreatment-emergent AE is any new sign or symptom, disease, or other untoward medical event that begins after written informed consent has been obtained but before the subject has received investigational product.

Elective treatment or surgery or preplanned treatment or surgery (that was scheduled prior to the subject being enrolled into the study) for a documented pre-existing condition that did not worsen from baseline is not considered an AE (serious or nonserious). An untoward medical event occurring during the prescheduled elective procedure or routinely scheduled treatment should be recorded as an AE or SAE.

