# 5.2 Definition of Serious Adverse Events

An SAE is any AE that:

- Results in death
- Is immediately life-threatening
- Requires inpatient hospitalisation or prolongation of existing hospitalisation

- Results in persistent or significant disability/incapacity
- Is a congenital anomaly/birth defect in offspring of the subject
- Is an important medical event that may jeopardise the subject or may require medical intervention to prevent one of the outcomes listed above

Medical or scientific judgment should be exercised in deciding whether expedited reporting is appropriate in this situation. Examples of medically important events are intensive treatment in an emergency room or at home for allergic bronchospasm, blood dyscrasias, or convulsions that do not result in hospitalisations; or development of drug dependency or drug abuse.

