## 5.5 Reporting of Serious Adverse Events

All SAEs have to be reported, whether or not considered causally related to the investigational product, or to the study procedure(s). All SAEs will be recorded in the eCRF.

If any SAE occurs in the course of the study, then Investigators or other site personnel inform the appropriate Sponsor representative(s) within one day ie, immediately but no later than 24 hours of when he or she becomes aware of it.

The designated Sponsor representative works with the Investigator to ensure that all the necessary information is provided to the Sponsor Patient Safety data entry site within 1 calendar day of initial receipt for fatal and life threatening events and within 5 calendar days of initial receipt for all other SAEs.

For fatal or life-threatening AEs where important or relevant information is missing, active follow-up is undertaken immediately. Investigators or other site personnel inform Sponsor representatives of any follow-up information on a previously reported SAE within one calendar day i.e., immediately but no later than 24 hours of when he or she becomes aware of it.

Once the Investigators or other site personnel indicate an AE is serious in the electronic data capture (EDC) system, an automated email alert is sent to inform the designated Sponsor representative(s).

If the EDC system is not available, then the Investigator or other study site personnel reports an SAE to the appropriate Sponsor representative by telephone. The Sponsor representative will advise the Investigator/study site personnel how to proceed.

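### The overall adverse-event rows include the pneumonia the drug is meant to prevent, and the readable SAP plans no subject-level rows without it

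*SAP*

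**What the plan says.** Protocol 2.2.1 names two primary endpoints. For efficacy it is "Incidence of nosocomial pneumonia caused by P aeruginosa through 21 days postdose"; for safety it is "Treatment-emergent AEs (TEAEs), treatment-emergent SAEs (TESAEs) and AESIs through 49 days postdose". The 21-day efficacy window lies wholly inside the 49-day safety window.

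Protocol 5.1 defines an AE as "Any untoward medical occurrence in a patient or clinical investigation subject administered a pharmaceutical product". The SAE criteria in 5.2 include death, immediate threat to life, and "Requires inpatient hospitalisation or prolongation of existing hospitalisation". Protocol 5.5 requires every SAE to be reported, whatever its cause. Protocol 1.1 says that pneumonia due to *P aeruginosa* "remains associated with significant mortality and morbidity, increased ICU and hospital length of stay, and substantial economic burden", so many cases can be expected to meet a seriousness criterion. Neither Protocol section 5 nor the readable SAP 3.8 makes an exception for endpoint events. No sentence says outright that an endpoint pneumonia is entered as an AE; that follows from the general definitions.

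Protocol 4.8.4.1 judges safety chiefly on TEAEs and TESAEs of any kind. SAP 3.8.1 turns this into a table: "The overall summary of AEs will summarise the number and percentage of subjects with at least one event". The same sentence adds rows for Grade 3 or higher, SAEs, death due to AEs, product-related events, product-related serious events and AESIs. SAP 3.8.1 to 3.8.3 also tabulate TEAEs, SAEs and fatal AEs by SOC and PT, and AESIs separately.

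**The concern.** The overall rows mix the outcome the drug should prevent with any harm it may cause. If MEDI3902 works, it lowers its own any-TEAE, Grade ≥ 3 and any-SAE percentages, and equal percentages in the two arms would then not mean equal safety. The readable SAP 3.8 plans no subject-level total from which endpoint pneumonia has been removed. What is at stake is the reading of a primary objective. An excess of other serious events spread thinly over many terms is what an overall row should pick up, and here that row can be offset by prevented pneumonias.

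**Working it through.** **Inputs.** From the Protocol Synopsis (Sample Size/Power Calculation) and SAP 2.4: placebo incidence 20%; relative reduction 50%, hence 20% × 0.5 = 10% on MEDI3902; two-sided α = 0.2; 80% power; 20% attrition; 143 per arm. The documents give no background rate b of SAEs other than *P aeruginosa* pneumonia, so b is varied from 30% to 90%.

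**The plan's own figure.** A pooled two-proportion calculation for 20% vs 10% gives 115 per arm, and 115 / 0.8 = 143.75, so 144 against the stated 143. A Wald test on the log relative risk, closer to the named Poisson method, gives 122, and 122 / 0.8 = 152.5, so 153. The contrast of 20% vs 10% is confirmed as the design effect, and nothing below depends on which formula was used.

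**Model.** Assume that every endpoint pneumonia is an SAE and is independent of other SAEs.

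- Any SAE on placebo: 1 − (1 − b) × 0.80
- Any SAE on MEDI3902, same b: 1 − (1 − b) × 0.90
- Built-in shift in favour of MEDI3902: 0.10 × (1 − b)
- Other-SAE rate b′ on MEDI3902 that makes the row equal: (1 − b′) × 0.90 = (1 − b) × 0.80, so b′ − b = (1 − b) × (0.10 / 0.90)

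| b (assumed) | Any SAE, placebo | Any SAE, MEDI3902 | Shift (points) | Excess that could be offset (points) | Subjects of 143 |
|---|---|---|---|---|---|
| 30% | 44.0% | 37.0% | 7.0 | 7.8 | about 11 |
| 50% | 60.0% | 55.0% | 5.0 | 5.6 | about 8 |
| 70% | 76.0% | 73.0% | 3.0 | 3.3 | about 5 |
| 90% | 92.0% | 91.0% | 1.0 | 1.1 | about 2 |

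**Half the endpoint events serious** (10% vs 5%): the offset excess is (1 − b) × (0.05 / 0.95), which is 3.7, 2.6, 1.6 and 0.5 points in the same order.

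**Without independence.** If every pneumonia subject also has another SAE, the shift is 0. If none does, it is 20 − 10 = 10 points.

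**Example.** Give MEDI3902 a true 5-point excess of other SAEs. The row then shows:

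- b = 30%: (1 − 0.65 × 0.90) − (1 − 0.70 × 0.80) = 41.5% − 44.0% = −2.5 points
- b = 50%: 59.5% − 60.0% = −0.5 points
- b = 70%: 77.5% − 76.0% = +1.5 points

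The sign reverses in the first two cases and the excess is diluted in the third.

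**Limits of the calculation.** It covers pneumonias within 21 days, because the design effect is stated for that window. It does not size the fatal-AE row, where only fatal pneumonias matter. For any TEAE the same algebra applies with that row's own background rate, so a rate near 100% leaves almost no shift.

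**The case against.** The best defence is that the plan already gives partial protection and that the size may be small.

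- **Other rows.** The same SAP 3.8.1 sentence plans subject-level rows for product-related events, product-related SAEs and AESIs. Protocol Appendix 2 calls an event not related when a clearly more likely explanation exists, such as a typical disease-related event, so pneumonia should largely drop out of the related rows. SOC rows aggregate over PTs, and pneumonia terms stay identifiable.
- **Background rate.** These are ventilated ICU patients, admissible with APACHE-II up to 24 and SOFA up to 11. SAP 3.5.1.2 expects death to be the main cause of missing primary data. A high b is plausible, and the effect is then small.
- **No decision rule.** The readable SAP 3.8 contains no safety hypothesis test and no rule that equal totals show equal safety.

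The second and third points stand as limits on size and consequence. The first stands in part. An excess concentrated in one term, one SOC or an AESI would be seen. The related rows, however, depend on the investigator's causality judgement. SOC and PT rows overlap within subjects, so they cannot be added up to a count of subjects with at least one SAE other than *P aeruginosa* pneumonia. Subtracting the efficacy result by hand is unreliable too: the endpoint and its onset are set by the adjudication committee (SAP 3.5.1.1), while AE rows rest on investigator-reported, coded terms (Protocol 5.4).

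A reader might infer that the design builds a 10-point advantage into every overall row. The documents do not support that. Ten points needs no overlap at all with other events in the row, and in the fatal-AE row it would need every pneumonia to be a fatal AE.

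**Conclusion.** The point holds for the composite rows of the overall AE summary. By the protocol's definitions the efficacy outcome falls within the TEAE and TESAE counts. If the drug works, and unless every pneumonia subject already has another event in the row, those counts are shifted in its favour. For any SAE at the design effect the shift is 7.0 to 1.0 points, and the excess it could offset is 7.8 to 1.1 points, as b runs from 30% to 90%. This rests on every endpoint event being serious and independent of other SAEs. The figures roughly halve if half the events are serious, and range from 0 to 10 points without independence.

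Two stronger readings are tempting but not supported. One is that the report as a whole would hide an excess of other serious events; the SOC/PT, related-event and AESI summaries would show a concentrated one. The other is that the DMC would be misled; the content of its outputs is left to a charter that is not among the documents. The table programming plan is also not visible, and the redacted SAP text lies before section 3.8, so no claim is made about either. This is an inexpensive improvement to the safety comparison. It does not touch the sample size.

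**What to change.** In SAP 3.8.1, keep the planned overall summary. Beside it, repeat four rows by arm (any TEAE, Grade ≥ 3, SAE, death due to AE) after removing AE records that match an adjudicated *P aeruginosa* pneumonia. Remove records, not subjects, so that the As-treated denominators do not change.

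State the matching rule, for example by subject, reported term and onset window. Where no adjudication exists, use the investigator-reported diagnosis. This matters late in follow-up, because Protocol 4.3.1.1 monitors for new pneumonia through Day 29 while safety runs to Day 50. State also that endpoint pneumonia is recorded as an AE, and as an SAE when it meets a criterion. Specify all this before unblinding.

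Interpret overall safety from both sets together. Resting the conclusion on the second set alone would displace the measure that Protocol 4.8.4.1 names.

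The cost is one extra table and the work of linking adjudicated events to AE records. No new data are needed and site reporting stays the same. Sequelae of pneumonia recorded under separate terms would remain in the second set, which is a further reason to read the two together.

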3.8.2 Adverse Events of Special Interest

Adverse events of special interest (AESI) will include targeted AEs of hypersensitivity (including anaphylaxis), infusion-related reactions, hepatic function abnormalities, and immune complex disease (eg, vasculitis, endocarditis, neuritis, glomerulonephritis, serum sickness, arthralgias) and will be summarized by treatment group and for MEDI3902 total

overall, and by SOC and PT based on MedDRA. Additional groupings may be added by the Medical Monitor if warranted.

An additional table will summarise duration and time to onset from dosing start for AESIs including hypersensitivity reactions, infusion related reactions and anaphylactic reactions.

3.8.3 Deaths and Treatment Discontinuations due to Adverse Events

AEs that resulted in death and AEs that led to discontinuation of study treatment will be summarized for each treatment group by SOC and PT.

3.8.4 Clinical Laboratory Evaluation

Laboratory parameters will be summarized for subjects in the As-treated population by treatment group and for MEDI3902 total as observed and change from baseline. Frequencies of worst observed toxicity and Grade 3-4 toxicities, as defined by [NCI CTCAE, 2010, v4.03](#), will be presented for each laboratory parameter by treatment group and for MEDI3902 total.

Also, laboratory parameters will be assessed by presenting tables containing information related to 2-grade (or greater) laboratory shifts from baseline.

For laboratory values reported as lower than the lower limit of quantification (LLOQ), a value equal to half of the limit of quantification will be imputed in the summaries. However, < LLOQ will be reported in the listings.

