# 4.1.3 Exclusion Criteria

Any of the following would exclude the subject from participation in the study:

- 1. Acute confirmed or suspected pseudomonal disease at study enrolment and investigational product dosing (endotracheal colonisation is acceptable and required [see inclusion criterion 5])
- 2. CPIS of  $\geq$  6 based on contributing parameters measured within past 24 hours, prior to investigational product dosing (Appendix 4).
- 3. Active pulmonary disease that would impair the ability to diagnose pneumonia, such as active tuberculosis or fungal disease, obstructing lung cancer, large pleural effusion or empyema, cystic fibrosis, or acute respiratory distress syndrome with lung "white out"
- 4. Subjects who are tracheostomy-dependent prior to current hospital admission
- 5. Receipt of anti-*P aeruginosa* antibiotics (as listed below) for > 72 hours within 96 hours prior to randomisation or anticipated ongoing receipt of the anti-*P aeruginosa* antibiotics:
  - Systemic colistin
  - Aerosolized colistin
- 6. Burns > 40% body surface area
- Acute Physiology and Chronic Health Evaluation-II (APACHE-II) score ≥ 25 or SOFA score ≥ 12 at time of randomisation (Appendix 5 and Appendix 6). Vasopressors only used to improve cerebral perfusion pressure (eg, subarachnoid hemorrhage) should not be used in the calculation of the cardiovascular component of the SOFA score.
- 8. Receipt of any investigational drug therapy within 30 days prior to investigational product dosing
- 9. Previous receipt of a mAb
- 10. Subjects with human immunodeficiency virus (HIV) infection, who in the opinion of the investigator, do not have well-controlled HIV infection. Subjects with a history of HIV infection who have been on highly active antiretroviral therapy and asymptomatic from HIV infection for at least 6 months may be enrolled.
- 11. Lymphoma not in complete remission and on chemotherapy
- 12. Recipients of bone marrow, stem cell, or solid organ transplant who are not currently in complete remission
- 13. Receipt of chemotherapy or other immunosuppressive drugs including glucocorticoid therapy (prednisone 20 mg or equivalent, daily or every other day for 30 days) in the past 2 months
- 14. History of known hypersensitivity to any component of the investigational product
- 15. Pregnant or nursing female

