#### 4.8.4.2 Analysis of Clinical Laboratory Parameters

Clinical laboratory measurements (ie, serum chemistry, and hematology) will be summarised from baseline through 21 days postdose.

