# Appendix 6 Sequential Organ Failure Assessment

#### Sequential Organ Failure (SOFA) Score European Society of Intensive Care Medicine (ESICM), 1994

SOFA score evaluate status of the following organ systems separately:

- 1. Respiration
- 2. Coagulation
- 3. Liver
- 4. Cardiovascular
- 5. Central Nervous System
- 6. Renal

Organ				SOFA	Score	
System	Measurement	0	1	2	3	4
Respiration	PaO 2 /FiO 2, mmHg	Normal	<400	<300	<200	<100
Coagulation	Platelets x10  /mm 	Normal	<150	<100	<50	<20
Liver	Bilirubin, mg/dL	Normal	1.2 -1.9	2.0-5.9	6.0-11.9	≥12.0
Cardiovascular	Hypotension	Normal	MAP <70 mHg	Dopamine $\leq 5$ or dobutamine (any dose)*	$\begin{array}{l} \text{Dopamine} > 5\\ \text{or epinephrine}\\ \leq 0.1 \text{ or}\\ \text{norepinephrine}\\ \leq 0.1 \end{array}$	Dopamine >15 or epinephrine > 0.1 or norepinephrine > 0.1
Central Nervous System	Glasgow Coma Score	Normal	13 -14	10-12	6-9	<6
Renal	Creatinine, mg/dL or	Normal	1.2 -1.9	2.0-3.4	3.5-4.9	≥5.0
	Urine output				<500 mL/day	<200 mL/day

\* adrenergic agents administered for at least 1 hour (doses given are in mcg/kg/min)

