3 STATISTICAL METHODS

3.1 General Considerations

Data will be provided in data listings sorted by treatment group and subject identification number (SID). Tabular summaries will be presented by treatment group. Categorical data will be summarized by the number and percentage of subjects in each category. Continuous variables will be summarized by descriptive statistics, including mean, standard deviation, median, minimum, and maximum. No multiplicity adjustments will be made to any of the analyses. In general, unless stated otherwise, baseline will be defined as the last value prior to dosing.

The key efficacy analyses will be based on Reda mg MEDI3902 and placebo subjects. Subjects who received Red mg MEDI3902 will be summarized descriptively for both efficacy and safety.

All statistical tests will be 2-sided at an alpha = 0.2 significance level unless stated otherwise.

Data analyses will be conducted using the SAS[®] System Version 9.3 or higher (SAS Institute Inc., Cary, NC) in a UNIX platform.

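### SAP 3.8.4 counts Grade 3-4 laboratory toxicity with no condition on the baseline grade and tabulates only shifts of two or more grades, so one-grade worsening is not shown as a shift and the Grade 3-4 contrast is diluted

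*SAP*

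**What the plan says.** SAP 3.8.4 (Clinical Laboratory Evaluation) plans three kinds of display for the As-treated population:

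- each parameter summarised "by treatment group and for MEDI3902 total as observed and change from baseline";
- "Frequencies of worst observed toxicity and Grade 3-4 toxicities, as defined by" CTCAE v4.03, by treatment group and for MEDI3902 total;
- "tables containing information related to 2-grade (or greater) laboratory shifts from baseline".

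The second display carries no condition on the baseline grade. The section does not say whether the worst observed grade excludes the pre-dose value. SAP 3.1 says that, in general, "baseline will be defined as the last value prior to dosing", and Protocol 4.8.4.2 says that laboratory measurements "will be summarised from baseline through 21 days postdose". No full table of baseline grade against worst grade is named.

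On entry severity, Protocol 4.1.3 item 7 excludes subjects by total score: APACHE-II of 25 or more, or a "SOFA score ≥ 12 at time of randomisation". No individual chemistry or hematology value is an exclusion criterion.

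**The concern.** Safety is one of the two primary objectives, and its endpoint is framed as treatment-emergent events (Protocol 2.2.1). For anti-drug antibodies, SAP 3.9 separates positivity at baseline from positivity afterwards. SAP 3.8.4 draws no such line for laboratory grades.

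That matters more in an ICU population than in most. A subject who enters at Grade 3 and stays there is counted as Grade 3-4. The table meant to bring in the baseline is filtered at two grades, so it cannot show any worsening in a subject who starts at Grade 3. What is at stake is how readily a reader of these tables would notice a real excess of laboratory worsening on drug.

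**Working it through.** **1. Can subjects enter with abnormal values?** Appendix 6 of the protocol scores platelets, bilirubin and creatinine from 0 to 4 each. Three points go to platelets below 50, bilirubin of 6.0-11.9 mg/dL or creatinine of 3.5-4.9 mg/dL. A total of 11 is still eligible, so one such component fits under the limit, and all three together (3 + 3 + 3 = 9) do as well. This shows that such entry values are possible, not how common they are. The CTCAE cut-offs are not in the documents, so I do not map SOFA points to CTCAE grades.

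**2. Which worsenings does each table show?** Between Grades 0 and 4 there are 4 + 3 + 2 + 1 = 10 possible worsenings. Six are shifts of two or more grades. The other four are:

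| Worsening | In the shift table? | New in the Grade 3-4 count? |
|---|---|---|
| 0 to 1 | no | no |
| 1 to 2 | no | no |
| 2 to 3 | no | yes, but not distinguishable from carry-over |
| 3 to 4 | no | no, already counted |

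All four can raise the worst-grade distribution, but without reference to where the subject started.

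**3. How much does carry-over dilute the Grade 3-4 contrast?** SAP 3.8.4 states no number to reproduce. The only design figure used is 143 per arm (SAP 2.4), which is not in dispute: 20% versus 10% at two-sided 0.2 and 80% power needs 115 per arm by the pooled two-proportion formula, and 115/0.8 = 143.75, or 144, against 143 stated.

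The remaining inputs are assumptions, because the documents give none:
- b is the share at Grade 3-4 at baseline, equal in both arms and all still counted;
- new Grade 3-4 occurs in 5% (placebo) and 15% (drug) of the rest;
- no baseline Grade 3 subject moves to Grade 4.

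Planned rates: b + (1 − b) × 0.05 and b + (1 − b) × 0.15.
Treatment-emergent rates: (1 − b) × 0.05 and (1 − b) × 0.15.
The difference is (1 − b) × 0.10 in both tables.

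Power is Φ[(d − 1.2816 × SE0)/SE1], with SE0 pooled and SE1 unpooled. At b = 20%:
- planned: d = 0.08, SE0 = 0.0531, SE1 = 0.0529, giving Φ(0.226) = 59%;
- treatment-emergent: d = 0.08, SE0 = 0.0321, SE1 = 0.0317, giving Φ(1.225) = 89%, or 90% if only subjects below Grade 3 at baseline are compared.

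| b | Planned table | Ratio | Treatment-emergent (ratio 3.0) | Difference in both, points | Power at 0.2, planned vs emergent |
|---|---|---|---|---|---|
| 2% | 6.9% vs 16.7% | 2.42 | 4.9% vs 14.7% | 9.8 | 90% vs 94% |
| 5% | 9.75% vs 19.25% | 1.97 | 4.75% vs 14.25% | 9.5 | 84% vs 93% |
| 10% | 14.5% vs 23.5% | 1.62 | 4.5% vs 13.5% | 9 | 75% vs 92% |
| 20% | 24% vs 32% | 1.33 | 4% vs 12% | 8 | 59% vs 89% |
| 30% | 33.5% vs 40.5% | 1.21 | 3.5% vs 10.5% | 7 | 48% vs 85% |

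With a smaller effect (5% versus 10%) and b = 20%, the planned table shows 24% versus 28%, a ratio of 1.17 instead of 2.0. Power is 31% instead of 56%.

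**The case against.** The strongest reply is that these tables are not the only view of laboratory worsening, and most of that reply stands.

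- **Change from baseline** is planned for every parameter, by arm and against randomised placebo. It keeps subjects with abnormal baselines. It averages over subjects, however, and does not count those who worsened.
- **Adverse events.** Under Protocol 5.1, "a finding judged by the investigator as medically significant should be reported as an AE". SAP 3.8.1 tabulates adverse events of Grade 3 or above, hepatic function abnormality is an AESI, and Appendix 9 sets up a Hy's law review. These channels carry the primary safety endpoint. The limits are that laboratory adverse events depend on investigator judgement, and the Hy's law criteria cover only transaminases and bilirubin.
- **Silence.** SAP section 1 leaves table detail to a separate Statistical Programming Plan, which may define worst grade as post-dose. That could answer the ambiguity about the baseline value. It would not remove the two-grade filter, which the SAP states outright. Nor would a post-dose rule alone remove subjects who enter at Grade 3 and stay there.
- **Power.** No test of these frequencies is planned, the rates are assumed, and 143 per arm ignores attrition. The power figures only translate lost precision into a familiar scale.

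A reader might infer that drug-related worsening would be invisible, or that carry-over shrinks the true difference between arms. The documents support neither. The displays above remain, and the table in the working shows the same absolute difference with and without carry-over.

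**Conclusion.** The point holds as a weakness in descriptive safety reporting. As SAP 3.8.4 is written, one-grade worsening is never displayed as a shift, and Grade 3 to 4 is also lost from the Grade 3-4 count. That part follows from the stated rules and needs no assumption.

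The dilution follows once some subjects enter at Grade 3-4, but its size cannot be taken from the documents. Under the assumptions shown, the displayed ratio falls from 3.0 to 2.42 at 2% carry-over and to 1.21 at 30%. The randomised comparison stays unbiased, and the absolute difference is the same as in a treatment-emergent table. That equality depends on no baseline Grade 3 subject reaching Grade 4. If some did, and more often in one arm, the treatment-emergent table would register it and the Grade 3-4 count would not.

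The primary efficacy analysis, alpha and sample size are untouched. The change is worth making because it is cheap.

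**What to change.** In SAP 3.8.4:

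1. Define the worst grade as the worst over post-dose values only.
2. Add a treatment-emergent Grade 3-4 count by arm: post-dose Grade 3 or 4 and higher than the subject's baseline grade. This picks up both 2 to 3 and 3 to 4.
3. Replace the two-grade filter with a full table of baseline grade by worst post-dose grade for each parameter and arm. Shifts of two or more grades can still be read from it.

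Make the Statistical Programming Plan match. The cost is SAP wording and a modest change to table programs on data already collected, with slightly longer output.
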